7.1.1. Liver Chemistry Stopping Criteria

Interrupting study drug based on liver test elevations in participants with normal or near-normal baseline liver tests

In study participants with normal or near-normal baseline liver tests (ALT, AST, and ALP $<1.5 \times$ ULN based on the normal limits determined by the testing laboratory), the study drug should be **interrupted** and close hepatic monitoring should be done if 1 or more of these conditions occur.

Elevation	Exception
ALT or AST $>8 \times$ ULN	
ALT or AST $>5 \times$ ULN for >2 weeks	
ALT or AST $>3 \times$ ULN and either TBL $>2 \times$ ULN or INR >1.5	For participants with Gilbert's syndrome: If baseline direct bilirubin is >0.5 mg/dL, then doubling of direct bilirubin should be used for drug interruption decisions rather than TBL $>2 \times$ ULN.
ALT or AST $>3 \times$ ULN with the appearance of fatigue, nausea, vomiting, right upper quadrant pain or tenderness, fever, rash, and/or eosinophilia ($>5\%$)	
ALP $>3 \times$ ULN, when the source of increased ALP is the liver	

Elevation	Exception
ALP $>2.5 \times$ ULN and TBL $>2 \times$ ULN	For participants with Gilbert's syndrome: If baseline direct bilirubin is >0.5 mg/dL, then doubling of direct bilirubin should be used for drug interruption decisions rather than TBL $>2 \times$ ULN.
ALP $>2.5 \times$ ULN with the appearance of fatigue, nausea, vomiting, right upper quadrant pain or tenderness, fever, rash, and/or eosinophilia ($>5\%$)	

Abbreviations: ALP = alkaline phosphatase; ALT = alanine aminotransferase; AST = aspartate aminotransferase; INR = international normalized ratio; TBL = total bilirubin; ULN = upper limit of normal (as determined by the testing laboratory).

Source: FDA Guidance for Industry: Drug-Induced Liver Injury: Premarketing Clinical Evaluation, July 2009 and other consensus guidelines, with minor modifications.

Interrupting study drug based on elevated liver tests in participants with abnormal baseline liver tests

In study participants with abnormal baseline liver tests (ALT, AST, and ALP $\geq 1.5 \times$ ULN), the study drug should be **interrupted** if 1 or more of these conditions occur.

Elevation	Exception
ALT or AST $>4 \times$ baseline	
ALT or AST $>3 \times$ baseline for more than 2 weeks	
ALT or AST $>2 \times$ baseline and either TBL $>2 \times$ ULN or INR >1.5	For participants with Gilbert's syndrome: If baseline direct bilirubin is >0.5 mg/dL, then doubling of direct bilirubin should be used for drug interruption decisions rather than TBL $>2 \times$ ULN.
ALT or AST $>2 \times$ baseline with the appearance of fatigue, nausea, vomiting, right upper quadrant pain or tenderness, fever, rash, and/or eosinophilia ($>5\%$)	
ALP $>2.5 \times$ baseline, when the source of increased ALP is the liver	
ALP $>2 \times$ baseline and TBL $>2 \times$ ULN	For participants with Gilbert's syndrome: If baseline direct bilirubin is >0.5 mg/dL, then doubling of direct bilirubin should be used for drug interruption decisions rather than TBL $>2 \times$ ULN.
ALP $>2 \times$ baseline with the appearance of fatigue, nausea, vomiting, right upper quadrant pain or tenderness, fever, rash, and/or eosinophilia ($>5\%$)	

Abbreviations: ALP = alkaline phosphatase; ALT = alanine aminotransferase; AST = aspartate aminotransferase; INR = international normalized ratio; TBL = total bilirubin; ULN = upper limit of normal (as determined by the testing laboratory).

Source: FDA Guidance for Industry: Drug-Induced Liver Injury: Premarketing Clinical Evaluation, July 2009 and other consensus guidelines, with minor modifications.

Resuming study drug after elevated liver tests

Resumption of the study drug can be considered only in consultation with the Lilly-designated medical monitor and only if the liver test results return to baseline and if a self-limited non-drug etiology is identified. Otherwise, the study drug should be discontinued.

7.1.2. Hypersensitivity Reactions

If the investigator determines that a systemic hypersensitivity reaction has occurred related to study intervention administration, the participant may be **permanently discontinued** from the study intervention, and the Sponsor's designated medical monitor should be notified.

If the investigator is uncertain about whether a systemic hypersensitivity reaction has occurred and whether discontinuation of study intervention is warranted, the investigator may consult the designated medical monitor from the study sponsor team.

7.1.3. Temporary Discontinuation

Criteria for temporary discontinuation of dulaglutide

The investigator may temporarily interrupt study treatment due to an AE, clinically significant variation in laboratory value, COVID-19 infection, hospital visits, travel, emergency surgery, hospitalization, or shortage of study treatment supply. Interruption in study treatment for 4 weeks or more will lead to permanent discontinuation of study treatment.

This will be allowed once at any time during the study. This information should be documented by the investigator. The study drug discontinuation decision will be taken post the titration in the initial 4-6 weeks of the study.

Guidance for temporary discontinuation of dulaglutide

Every effort should be made by the investigator to maintain participants in the study and to restart dulaglutide promptly, as soon as it is safe to do so.

Participants will continue their study visits and follow-up according to the SoA.

Participants should resume the dose prescribed before the temporary dosing interruption or as advised by the investigator.

Recording temporary discontinuation of dulaglutide

The dates of dulaglutide interruption and restart must be documented in source documents and entered in the CRF.

Participant noncompliance should not be recorded as interruption of dulaglutide in the CRF.

7.2. Participant Discontinuation/Withdrawal from the Study

Discontinuation is expected to be uncommon.

A participant may withdraw from the study

- at any time at the participant's own request
- at the request of the participant's designee (for example, parents or legal guardian)
- at the discretion of the investigator for safety, behavioral, compliance, or administrative reasons
- if enrolled in any other clinical study involving an IP or enrolled in any other type of medical research judged not to be scientifically or medically compatible with this study
- if the participant, for any reason, requires treatment with a therapeutic agent that is prohibited by the protocol and has been demonstrated to be effective for treatment of the study indication. In this case, discontinuation from the study occurs prior to introduction of the new agent, and
- if a study participant is diagnosed with any type of diabetes mellitus other than T2D.

At the time of discontinuing from the study, if possible, the participant will complete procedures for an early discontinuation visit and posttreatment follow-up, as shown in the SoA. If the participant has not already discontinued the study intervention, the participant will be permanently discontinued from the study intervention at the time of the decision to discontinue the study.

If the participant withdraws consent for disclosure of future information, the Sponsor may retain and continue to use any data collected before such a withdrawal of consent. If a participant withdraws from the study, the participant may request destruction of any samples taken and not tested, and the investigator must document this in the site study records.

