7.1. Discontinuation of Study Intervention

When necessary, a participant may be permanently discontinued from study intervention. If so, the participant will remain in the study and follow procedures for remaining study visits, as shown in the SoA.

Participants who stop dulaglutide permanently may receive another glucose-lowering medication at the investigator discretion. The new glucose-lowering medication will be recorded on the appropriate CRF.

A participant should be permanently discontinued from study intervention if the participant

- becomes pregnant during the study
- requests to discontinue dulaglutide
- did not take dulaglutide for more than 4 consecutive weeks or missed more than 4 consecutive doses of dulaglutide at any time during the study
- is inadvertently enrolled (this would be decided in consultation with the Sponsor's medical officer), or
- should permanently discontinue the study intervention for safety reasons, in the opinion of the investigator.

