8.3.1. Timing and Mechanism for Collecting Events

This table describes the timing, deadlines, and mechanism for collecting events.

Event	Collection Start	Collection Stop	Timing for Reporting to Sponsor or Designee	Mechanism for Reporting	Back-Up Method of Reporting
Adverse Event					
AE	Signing of the ICF	The last safety follow-up visit	As soon as possible upon site awareness	AE CRF	N/A
Serious Adverse Event					
SAE and SAE updates – prior to start of study intervention and deemed reasonably possibly related to study procedures	Signing of the ICF	Start of intervention	Within 24 hours of awareness	SAE paper form	SAE paper form
SAE and SAE updates – after start of study intervention	Start of intervention	The last safety follow-up visit	Within 24 hours of awareness	SAE paper form	SAE paper form
SAE ^a – after participant's study participation has ended and the investigator becomes aware	After participant's study participation has ended	N/A	Promptly	SAE paper form	N/A
Pregnancy					
Pregnancy in female participants and female partners of male participants	After the start of study intervention	90 days after the last dose	Within 24 hours (see Section 8.3.2)	Pregnancy paper form	Pregnancy paper form
Product Complaints					
PC associated with an SAE or might have led to an SAE	Start of study intervention	End of study intervention	Within 24 hours of awareness	PC form	N/A
PC not associated with an SAE	Start of study intervention	End of study intervention	Within 1 business day of awareness	PC form	N/A
Updated PC information	—	—	As soon as possible upon site awareness	Originally completed PC form with all changes signed and dated by the investigator	N/A

Event	Collection Start	Collection Stop	Timing for Reporting to Sponsor or Designee	Mechanism for Reporting	Back-Up Method of Reporting
PC (if investigator becomes aware)	Participation in study has ended	N/A	Promptly	PC form	

Abbreviations: AE = adverse event; CRF = case report form; ICF = informed consent form; N/A = not applicable; PC = product complaint; SAE = serious adverse event.

a SAEs should not be reported unless the investigator deems them to be possibly related to study treatment or study participation.

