10.7. Appendix 7: Abbreviations and Definitions

Term	Definition
abuse	Use of a study intervention for recreational purposes or to maintain an addiction or dependence
AE	adverse event
ALP	alkaline phosphatase
ALT	alanine aminotransferase
AST	aspartate aminotransferase
AWARD	Assessment of Weekly AdministRation of LY2189265 in Diabetes
BG	blood glucose
BMI	body mass index
CDSCO	Central Drugs Standard Control Organisation
CFR	Code of Federal Regulations
CI	confidence interval
CKD-EPI	chronic kidney disease-epidemiology
complaint	A complaint is any written, electronic, or oral communication that alleges deficiencies related to the identity, quality, purity, durability, reliability, safety or effectiveness, or performance of a drug or drug delivery system.
compliance	Adherence to all study-related, good clinical practice (GCP), and applicable regulatory requirements.
COVID-19	coronavirus disease 2019
CRF	case report form
	A printed, optical, or electronic document designed to record all of the protocol-required information to be reported to the Sponsor for each trial participant.
CRO	contract research organization
CTA	clinical trial agreement
Data monitoring committee	A data monitoring committee, or data monitoring board is a group of independent scientists who are appointed to monitor the safety and scientific integrity of a human research intervention, and to make recommendations to the Sponsor regarding the stopping of a study for efficacy, or for harms, or for futility. The composition of the committee is dependent upon the scientific skills and knowledge required for monitoring the particular study.

DBP	diastolic blood pressure
ECG	electrocardiogram
eCRF	electronic case report form
EDC	electronic data capture system
eGFR	estimated glomerular filtration rate
enroll	The act of assigning a participant to a treatment. Participants who are enrolled in the study are those who have been assigned to a treatment.
enter	Participants entered into a study are those who sign the informed consent form directly or through their legally acceptable representatives.
FAS	full analysis set
FBG	fasting blood glucose
GCP	good clinical practice
GI	gastrointestinal
GLP-1 RA	glucagon-like peptide-1 receptor agonist
HbA1c	hemoglobin A1c
IB	investigator's brochure
ICF	informed consent form
ICH	International Council for Harmonisation
IEC	independent ethics committee

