A participant will be considered lost to follow-up if he or she repeatedly fails to return for scheduled visits and is unable to be contacted by the study site. For participants who fail to return for a scheduled visit or were otherwise unable to be followed up by the site, the site personnel or designee is expected to make diligent attempts to contact till 4 weeks from the scheduled visit.

The following parameters will be summarised for the subject's disposition table as per eCRF:

- Number of total screened subjects
- Number of screen failure subjects
- Reason of screen failure subjects
- Number of screen positive subjects
- Subjects who are screened positive but did not receive treatment
- Number of Subject's in Enrolled Analysis set
- Number of Subject's in Full Analysis set
- Number of Subject's in per-protocol analysis set
- Number of Subject's in safety analysis set
- Number of subject's completed trial

- Number of Subject's Completed All Weekly Doses Within Treatment Period
- Number of subjects received 1.5 mg only
- Number of subjects received 0.75 mg only
- Number of subjects with any dose modification* (* subjects who have received at least one dose of 1.5 mg and at least one dose of 0.75 mg)
- Number of subjects withdrew early prior to receiving treatment
- Number of subjects withdrew early from trial
- Subjects who are screened positive but did not receive treatment

The following parameters will be summarised for the early withdrawals table as per eCRF Subject's primary reason for discontinuation (reasons mentioned in eCRF "End of the Study" form) which is as follows:

- Adverse event
- Death
- Lost to follow-up
- Pregnancy
- Protocol violation
- Screen failure
- Consent withdrawal not due to an adverse event
- Site terminated by sponsor
- Study terminated by sponsor
- Withdrawal by sponsor
- Migration from the study site such that follow up visits are not possible
- Other

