14.2 Analysis

Population: SAF and PP

Stratification: Table: Add the strata as needed in case subjects with dose modification exceeding 20% based on enrolled population as per section 7.3:

a. Subjects on 1.5 mg only by ATC and PT

b. Subjects on 0.75 mg only by ATC and PT

c. Subjects with any dose modification* by ATC and PT

* Subjects who have received at least one dose of 1.5 mg and at least one dose of 0.75 mg

Listing: By subject

Statistics: Prior and concomitant medication will be summarized separately as (frequency, percentages) for table and listing will be presented.

15. Adverse events**15.1 Variables and derivations**

Adverse Events (AEs) will be coded using MedDRA central coding dictionary, Version (refer to DMP for dictionary version).

For the definition of Adverse events (AE) and Serious adverse event (SAE) refer to the protocol section 10.3.

TEAEs are defined as events that are newly reported after the first study drug treatment or are reported to have worsened in severity after the first study drug treatment.

In section 24 Appendix 2 the algorithm is given for calculation of partial date imputation for adverse events (AEs), and it will be used for partially missing adverse event start and end date imputation.

The following parameters will be summarised for the overview of participants' adverse events:

- Any AEs
- Any TEAEs
- Related TEAEs
- Severity of TEAEs (Mild, Moderate, Severe, Life threatening and Death)
- Outcome of AEs (Recovered or resolved, Recovering, or resolving, Not recovered or not resolved, Recovered, or resolved with sequelae, Fatal and Unknown)
- Serious AEs
- AEs leading to Discontinuation from the study
- AEs leading to Death
- Related AEs leading to Death

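### Protocol 7.2 permits withdrawal from the study for safety without marking it as an exception to 7.1, so new AEs and unrelated SAEs before Week 24 can go unrecorded

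*Protocol*

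**What the plan says.** **Stopping drug (Protocol 7.1).** For a patient permanently taken off dulaglutide: "If so, the participant will remain in the study and follow procedures for remaining study visits, as shown in the SoA". The listed reasons include a patient who "should permanently discontinue the study intervention for safety reasons, in the opinion of the investigator". Missing more than 4 consecutive doses is another.

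**Leaving the study (Protocol 7.2).** Exit is called uncommon, and one permitted route is "at the discretion of the investigator for safety, behavioral, compliance, or administrative reasons". On exit, "if possible, the participant will complete procedures for an early discontinuation visit and posttreatment follow-up, as shown in the SoA".

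**Event collection (Protocol 8.3 and 8.3.1).** AEs are collected up to the last safety follow-up visit. Once participation has ended, only SAEs that the investigator learns of are taken, with the footnote "SAEs should not be reported unless the investigator deems them to be possibly related to study treatment or study participation". Section 8.3 keeps the investigator responsible for following events that are serious, related, or led to discontinuation.

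**Endpoint.** Protocol Section 3 and SAP 18.2.1 count AEs and SAEs from baseline to Week 24, whatever their cause. Protocol 9.3 and 9.4.2 assign the safety endpoints to the safety set.

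**SAP handling.** SAP 10.1 lists reasons that "will be summarised for the early withdrawals table as per eCRF", Adverse event among them. SAP 15.1 has an overview row for "AEs leading to Discontinuation from the study" but none for AEs leading to stopping drug. SAP 18.1.2 models deaths, SAEs and TEAEs over the study period with log treatment exposure time as offset. SAP 12.1 defines duration of exposure as running from first to last administration.

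**The concern.** The same person, the investigator, acting for the same reason, safety, can apply either rule, and the follow-up differs sharply. Under 7.1 the patient is contacted through Week 28. Under 7.2 observation may end at exit. No sentence says that 7.2 yields to 7.1 when the reason is safety, so two sites could treat the same patient differently and both follow the protocol.

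Compliance raises the same question less clearly. The glossary defines it as "Adherence to all study-related, good clinical practice (GCP), and applicable regulatory requirements", which is wider than missed doses, and 7.1 has its own missed-dose rule. A site could still use the compliance ground in 7.2 for a patient who stopped injecting.

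At stake is the completeness of the all-cause safety record in a trial whose primary objective is safety. The patients concerned leave for reasons that may be connected with how they tolerate the drug, so the loss need not be random.

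**Working it through.** **1. The two routes side by side.** Take a patient whose last dose is at Week 8.

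| | Protocol 7.1 | Protocol 7.2 |
|---|---|---|
| Wording | directive | permission |
| Contacts left | Weeks 12, 16, 20, 24, 28 | closing visit and follow-up, where possible |
| New non-serious AE, Weeks 12 to 24 | recorded | not collected |
| New unrelated SAE or death, Weeks 12 to 24 | recorded | not reportable |
| Weeks unobserved before Week 24 | 0 | 24 − (8 + 4) = 12 with the 4-week follow-up; 24 − 8 = 16 without |

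For last doses at Weeks 4 and 12 the unobserved time is 16 and 8 weeks with follow-up, or 20 and 12 without. The vital-status search in 7.3 does not close the gap: it sits under loss to follow-up and refers to randomly assigned participants, of whom this trial has none.

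**2. The plan's own numbers (Protocol 9.6).** 250 × 0.80 = 200 treated; 200 × 0.80 = 160 at the end; so 40 dropouts are allowed for. They are not split by reason, so the number of investigator-initiated safety exits cannot be derived.

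**3. Crude proportions in the safety set.** Leavers stay in the denominator, so a missed first event can only lower the proportion. Per patient: 1/200 = 0.5 point. If 1 to 5 patients are affected (assumed): 0.5 to 5/200 = 2.5 points. The low end is more likely for any AE: Protocol 4.2 says GI events usually come early, and a patient who leaves because of an AE is already counted. The same 0.5 point applies to the SAE proportion per patient whose first SAE is missed.

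**4. Scale for SAEs.** Assumptions: k patients exit with last dose at Week 8, the 4-week follow-up is done, and the SAE rate r is 0.05 to 0.20 per patient-year.

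- Full window: 200 × 168/365.25 = 92.0 patient-years.
- Unobserved: k × 84/365.25, which is 1.15 patient-years (1.2%) for k = 5 and 4.60 (5.0%) for k = 20.
- Expected patients with a new SAE in that time: k × (1 − exp(−r × 84/365.25)), which is 0.06 to 0.22 for k = 5 and 0.23 to 0.90 for k = 20. Those judged unrelated would not be reportable.

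**5. The negative binomial offset.** This arises under 7.1 as it stands, because patients off drug remain under observation. Assume 24 weeks of exposure for everyone else, k patients stopped at Week 8 and observed to Week 24, and equal event rates on and off drug.

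- Observation: 200 × 24 = 4,800 patient-weeks.
- Exposure: (200 − k) × 24 + k × 8, which is 4,720 for k = 5 and 4,480 for k = 20.
- Inflation of the annual rate: 4,800/4,720 = 1.017 and 4,800/4,480 = 1.071, or about 1.7% and 7.1%.

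**The case against.** The strongest reply is that there is no real conflict. Section 7.1 is mandatory and 7.2 only permits. The liver, hypersensitivity and interruption rules (7.1.1 to 7.1.3) act on study drug, and the opening of Section 8 frames immediate safety concerns as a decision about study intervention. Section 7.2 itself separates stopping drug from leaving. This stands, and it is why 7.1 is treated here as the apparent default. It does not remove the gap, because 7.2 names safety as a reason to leave and says nothing about when that applies.

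A reader might infer from the SAP that investigator withdrawal for safety is planned for. The documents do not show that. The reason list in SAP 10.1 has both Adverse event and a consent-withdrawal code limited to cases not due to an AE, so the first code fits a patient who leaves at their own request because of an AE. The SAP 15.1 row fits the same reading, and Protocol 9.4.5 plans analyses of discontinuations due to AEs without limiting them to study exit.

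A reader might also infer that 7.2 removes patients, with AEs already recorded, from the primary tables. That can happen where someone exits without an on-study HbA1c, but it comes from SAP 18 using the FAS where Protocol 9.3 and 9.4.2 specify the safety set. It is a separate inconsistency, telephone follow-up would not repair it, and no figure for it is counted here.

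Three limits also stand:
- Events already reported that are serious, related or led to discontinuation remain under follow-up through 8.3, so the loss concerns new events.
- The rule in 8.3.1 applies equally to patients who leave of their own accord.
- Exposure-adjusted incidence and censoring in the GI time-to-event analyses allow for shorter follow-up. They do not recover unrecorded events, and the crude proportions have no such adjustment.

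**Conclusion.** The point holds as a gap in wording, not as a contradiction. A site can follow the plan, withdraw a patient for safety, and lose new non-serious AEs and unrelated SAEs or deaths inside the Week 0 to 24 window. In safety-set tables the crude proportions can only be too low, by 0.5 point per patient missed. The number of such patients is not in the documents. Because 7.2 expects exits to be uncommon and GI events come early, the effect on the overall AE proportion is probably small. The ranges above rest on assumed counts, exit times and rates. The mismatch between events and exposure time in SAP 18.1.2 is present already, and its size depends on how many patients stop drug and stay in the study.

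**What to change.** 1. **Protocol 7.2.** State that stopping dulaglutide for safety, or for non-compliance with study drug, is not in itself a reason to leave the study and follows 7.1. The investigator may still end on-site visits or procedures that are unsuitable for the patient. AE, SAE and vital-status collection then continues by telephone through Visit 801 unless the participant withdraws consent.
2. **SAP 18.1.2.** Count events and time over the same window in the negative binomial models: both on treatment, or both over the observation period.

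The cost is wording plus a few contacts. A patient stopped at Week 8 has five left, of which Weeks 12 and 24 are scheduled on site and could become calls; the others are already remote. For an assumed 5 to 20 patients that is 5 × 5 = 25 to 5 × 20 = 100 contacts. The downside is that some off-drug events will appear in the study-period tables, which makes the second change more necessary.

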1.3. Schedule of Activities (SoA)

	Screening	Treatment Period							Follow-Up	Comments
		1	2	3	4	5	6	7		
Visit Number	1	2	3	4	5	6	7	8	801	
Weeks from Start of Treatment	-2	0	4	8	12	16	20	24	28	
Visit Interval Tolerance (days)	±3	—	±3	±3	±3	±3	±3	±3	±3	
Visit Detail	F	F	T	T	F	T	T	F	T	T=telehealth visit F=fasting visit
Informed consent	X									The ICF must be signed by patients or their caregivers before any -protocol specific tests or procedures are performed. See Section 10.1.3 for additional details.
Inclusion or exclusion criteria, review, and confirm	X	X								The Investigator will confirm inclusion and exclusion criteria prior to enrollment and administration of first dose of study intervention.
Demographics	X									Includes ethnicity (where permissible), year of birth, gender, and race
Preexisting conditions and medical history, including relevant surgical history	X									Collect all ongoing conditions and relevant past surgical and medical history
Prespecified medical history (indication and history of interest)	X									
Prior treatments for indication	X									

Concomitant medications	X	X	X	X	X	X	X	X		
AEs	X	X	X	X	X	X	X	X	AEs are any events that occur after signing the informed consent. These will also include any AE reported after the first dose of dulaglutide.	
Hypoglycemia events	X	X	X	X	X	X	X	X	Clinical assessment based on participant history and diary entries	
Physical Evaluation										
Height	X								Participant should remove shoes.	
Weight	X	X			X			X		
Vital signs	X	X			X			X	Includes temperature, blood pressure, and pulse rate. Measure 3 times, using the same arm, after participant has been sitting at least 5 min and before ECG tracing and collection of blood samples for laboratory testing. Of the 3 measurements, the blood pressure and pulse rate values observed during the third and final measurements will be entered in the eCRF. Additional vital signs may be measured as necessary at investigator's discretion.	
Physical examination	X								This includes examination for any sensory loss, motor neuropathy, and retinopathy. Additional physical	

										examinations may be completed as necessary at investigator's discretion.
12-lead ECG (local)	X									Participants should be supine for approximately 5-10 min before ECG collections and remain supine but awake during the ECG collection. ECGs may be repeated at the investigator's discretion at any visit.

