9.3. Analyses Sets

For purposes of analysis, the following populations are defined:

Participant Analysis Set	Description
Enrolled	
 All participants who sign informed consent form and are screen positive
FAS	
 All patients who received at least 1 dose of study treatment and have at least 1 measurement of HbA1c after study treatment
Per-protocol set	
All patients in the FAS who meet the following criteria
 
 have no important protocol deviations that could impact the assessment of the primary objective (see SAP) are at least 80% compliant with the study drug in terms of dose taken have no instance of deviation from persistence with study drug in terms of no more than the 15 days gap between 2 consecutive doses complete the treatment phase (24 weeks) for the primary endpoint
Safety analysis set	
 All patients who received at least 1 dose of study treatment

Abbreviations: FAS = full analysis set; HbA1c = hemoglobin A1c; SAP = statistical analysis plan.

The FAS is used to analyze endpoints related to the efficacy objectives, and the safety analysis set is used to analyze the endpoints and assessments related to safety.

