9.4.3. Secondary Endpoints Analysis

Change in HbA1c from baseline to 24 weeks of therapy with dulaglutide 1.5 or 0.75 mg

The change in HbA1c level from baseline to Weeks 12 and 24 for all available data including post-rescue medication values will be analyzed using descriptive statistics (mean, median, SD, SE, minimum, maximum, and number with missing values). In addition, for the actual value and change from baseline, a descriptive analysis using LOCF will be performed, using the baseline or 12-week value, if the 24-week value is missing or occurred after use of rescue medication.

For subjects requiring rescue medication (see Section 6.1.1), HbA1c values recorded after the first administration of rescue medication will not be considered for analysis, and these values will be considered as missing. The MMRM, as described in Section 9.4.1 will be used for analysis of the change in HbA1c level from baseline to Weeks 12 and 24.

If convergence is not met in the MMRM, the change in HbA1c level from baseline to Week 24 will be analyzed using the general linear model for the FAS population. The general linear model will evaluate the change from baseline in HbA1c level as the dependent variable and the baseline value of HbA1c as covariate. The LOCF method of missing value imputation will be used.

FAS population will be used for analysis as per planned treatment.

The analyses will be repeated for the per-protocol population.

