6.2 Full Analysis Set (FAS)

All patients who received at least 1 dose of study treatment and have at least 1 measurement of HbA1c after study treatment.

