23.9 Presentation of visits

- Visit 1 (Week -2) Screening
- Visit 2 (Week 0)

- Visit 3 (Week 4)
- Visit 4 (Week 8)
- Visit 5 (Week 12)
- Visit 6 (Week 16)
- Visit 7 (Week 20)
- Visit 8 (Week 24)
- Visit 801 (Week 28) Follow up

CCI

CCI

CCI

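### Protocol 7.2 relies on an early discontinuation visit that the Schedule of Activities lacks, so patients who withdraw from the study before Week 12 normally fall outside the FAS that the SAP uses for the primary AE endpoints

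*Protocol*

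**What the plan says.** - **Withdrawal.** Under Protocol 7.2, on leaving the study and if possible, "the participant will complete procedures for an early discontinuation visit and posttreatment follow-up, as shown in the SoA". Protocol 7.1 treats stopping the drug separately: those patients stay in the study and keep their remaining visits.
- **Schedule.** The columns of Protocol 1.3 are Visits 1 to 8 and 801, fixed by "Weeks from Start of Treatment". None is tied to withdrawal, and no comment describes an exit visit. Visit 801 is marked T in a row whose key reads "T=telehealth visit F=fasting visit". SAP 23.9 gives the same list, ending with "Visit 801 (Week 28) Follow up".
- **Measurements.** After baseline, the SoA places HbA1c, FBG, weight, vital signs, hematology and chemistry at Visits 5 and 8 only. Protocol 9.4.3 matches this: "The change in HbA1c level from baseline to Weeks 12 and 24".
- **Analysis sets.** Protocol 9.3 defines the FAS as "All patients who received at least 1 dose of study treatment and have at least 1 measurement of HbA1c after study treatment", and SAP 6.2 repeats the condition ("have at least 1 measurement of HbA1c after study treatment"). The safety set needs one dose only. Protocol 9.3 adds that "the safety analysis set is used to analyze the endpoints and assessments related to safety", and Protocol 9.4.2 names the safety population for AE frequencies. SAP 18.1.2, 18.2.2 and 18.3.2 instead name FAS and PP for all three primary AE endpoints.
- **Off-schedule and missing values.** SAP 7.1 keeps unscheduled values out of by-visit summaries and does no windowing. The LOCF rules in SAP 8.2, 16.2 and 19.1.2 draw only on the baseline or Week 12 value.

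**The concern.** The cross-reference in Protocol 7.2 leads nowhere, so sites have no list of what to do when a patient leaves. For a patient who leaves before Visit 5, the missing list also affects the analysis: without an HbA1c after treatment, the patient is outside the FAS, and the SAP reports the primary AE endpoints in the FAS and in the PP set, which is a subset of it. A treated patient who withdrew in the first weeks would be absent from the main tables of a study whose purpose is to describe safety. Protocol 4.2 says that gastrointestinal effects usually occur early in therapy, so it is plausible that some of these patients left because of them. The laboratory summaries have a separate problem, because carrying baseline forward records no change for someone who was never measured again.

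**Working it through.** **1. The plan's own figures (Protocol 9.6).** Treated: 250 × (1 − 0.20) = 200. Completers: 200 × (1 − 0.20) = 160. Planned dropouts: 200 − 160 = 40. The stated 200 and 160 reproduce.

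**2. What each type of leaver contributes under the current schedule.**

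| Patient | HbA1c, FBG, weight, vital signs, hematology, chemistry after baseline | In FAS? | In safety set? |
|---|---|---|---|
| Stops drug, stays in study | Still scheduled at Weeks 12 and 24 | Yes, once an HbA1c is taken | Yes |
| Leaves study between Weeks 12 and 24 | Week 12 values; no exit value | Yes | Yes |
| Leaves study before Week 12 | None scheduled | Normally no | Yes |

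AEs and hypoglycemia are collected at the Week 4 and Week 8 telehealth visits for patients still in the study. The third row therefore lacks the listed measurements but not all follow-up data.

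**3. Number affected.** The documents do not say when dropouts leave. Let s be the share of the 40 who leave before Week 12. Lost from the FAS = 40 × s; FAS = 200 − 40 × s.

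| s (assumed) | Lost | % of 200 | FAS |
|---|---|---|---|
| 0 | 0 | 0% | 200 |
| 0.25 | 10 | 5% | 190 |
| 0.50 | 20 | 10% | 180 |
| 0.75 | 30 | 15% | 170 |
| 1 | 40 | 20% | 160 |

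A constant dropout hazard over 24 weeks gives 200 × (1 − √0.8) = 21.1, close to the middle row.

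**4. What this could do to an AE proportion (AE rates assumed).** Suppose 50% of FAS patients have an AE.
- If all 20 early leavers also had one, the safety-set figure is (0.5 × 180 + 20)/200 = 55%, against 50% in the FAS.
- At the extreme of 40 early leavers, all with an AE, it is (0.5 × 160 + 40)/200 = 60%.
- If early leavers have the same 50% rate, the two sets agree.

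**5. Precision.** The 95% half-width at 50%, by the normal approximation 1.96 × √(0.25/n), is 6.9 points at n = 200, 7.3 at 180 and 7.7 at 160. The issue is who is left out, not the loss of sample size.

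**6. Laboratory tests.** These are summarised in the safety set (SAP 16.2), so a patient who leaves before Week 12 is included. With Week 12 and Week 24 both missing, LOCF takes baseline, and the change is baseline − baseline = 0. In the observed change from baseline the same patient is absent, because SAP 7.5 requires a post-baseline value.

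**7. Whether an improvised exit sample closes the gap.** Only in part. It would meet the FAS wording, which does not require a scheduled value. It would still be left out of by-visit summaries, and LOCF would still use baseline.

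**The case against.** The strongest reply is that Protocol 7.2 does ask for the visit, Protocol 10.2 allows additional tests at any time, and the FAS accepts any HbA1c after treatment, so a careful site could keep such a patient in the FAS. That stands: loss from the FAS is the normal outcome, not a certain one.

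A second reply is that the loss of AEs comes from the SAP's choice of population rather than from the missing visit. Every treated patient is in the safety set, and SAP Section 15 tabulates TEAEs, SAEs and deaths there. This also stands, and it is why the fix must include the analysis set: a visit held only if possible cannot recover everyone.

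A third is that an HbA1c taken a few weeks after the first dose represents neither Week 12 nor Week 24. That is right, and it limits how the value may be used.

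A reader might infer more than the documents support:
- **That all early leavers drop out of the FAS.** Those who leave after Week 12 already have a qualifying HbA1c.
- **That patients who stop the drug for intolerance are lost.** Protocol 7.1 keeps them on the schedule.
- **That early leavers have no data after baseline.** AEs and hypoglycemia are collected at Weeks 4 and 8.
- **That the results are shown to be biased toward patients who did well.** The withdrawal reasons in SAP 10.1 include migration, site closure and consent withdrawal unrelated to an AE. The documents give neither the timing nor the mix of reasons, so the direction is plausible but not established.

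**Conclusion.** The plan is internally inconsistent: Protocol 7.2 depends on a visit that neither the SoA nor the SAP defines. The consequence is confined to patients who withdraw from the study itself before Week 12. The supportable range is the full 0 to 40 in the table; the figure of 20 rests on an assumed even split. The possible distortion of the primary AE proportions depends on assumed AE rates and is nil if early leavers resemble the rest. For patients who leave later, the only loss is a value at exit. The correction should be made because it is inexpensive, the protocol already promises the visit, and the SAP's use of the FAS for AEs departs from the protocol although SAP Section 5 reports no change to the planned analyses.

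**What to change.** 1. **SoA.** Add an early discontinuation column with AEs, hypoglycemia, HbA1c, FBG, weight, vital signs, hematology and chemistry, done if the participant agrees. Cost: a schedule amendment and one blood draw per consenting leaver.
2. **SAP.** State that the exit value counts as a post-baseline measurement, is summarised as an exit value, and is an allowed LOCF source. Do not relabel it as Week 12 or Week 24 in the MMRM. Add the visit to SAP 23.9. Cost: a short text change and some programming.
3. **Primary AE endpoints.** In SAP 18.1 to 18.3, replace the FAS by the safety analysis set, in line with Protocol 9.3 and 9.4.2. This needs no new data and protects the AE tables even when a leaver does not attend the exit visit.
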